2.0 Rationale and Specific Aims

Figure 1. Conceptual Framework of the Proposed Clinical Trial

Cardiovascular disease (CVD) is a top public health concern in the U.S. CVD is highly prevalent and is the number one killer of Americans. Moreover, its economic burden is substantial and on the rise.^{1,2} Thirty years of evidence indicates that adults with depression are at increased risk of CVD events and poor CVD prognosis;^{8,9} however, attempts to improve the CVD outcomes of depressed patients have been unsuccessful. The few trials^{21-23,30-32} that have evaluated whether depression interventions reduce the likelihood of CVD events generally have not observed the anticipated benefits. The reasons for these null results have been the subject of debate.³⁴ We recently proposed a novel explanation: the depression interventions in these trials, all of which involved patients with preexisting CVD, may have been delivered too late in the natural history of CVD.¹³ We hypothesized that treating depression before, versus after, the onset of clinical CVD could reduce CVD risk because: (1) earlier treatment of another CVD risk factor, hypercholesterolemia, yields more pronounced benefits,⁴¹⁻⁴⁴ (2) depression exerts a cardiotoxic influence early in CVD pathogenesis,^{17,19,51,53} (3) depression treatments appear to have greater antidepressive efficacy prior to clinical CVD onset,^{36,54} and (4) conventional prognostic factors may override depression's harmful effect during the later stages of CVD.^{16,61}

As a first step, we conducted an 8-year follow-up study³⁵ of Indiana sites of the Improving Mood-Promoting Access to Collaborative Treatment (IMPACT) trial,³⁶ in which older depressed patients were randomized to a collaborative care intervention or usual care. Results supported our hypothesis. Intervention patients without baseline CVD had a 48% lower risk of myocardial infarction (MI) or stroke than usual care patients. There was no treatment effect among patients with baseline CVD. Although these results are unique and potentially significant, the IMPACT trial was not designed to test our hypothesis. Thus, our findings are post hoc and observational, CVD outcomes were not pre-specified endpoints, and virtually no mechanistic data were collected. To address these key limitations, there is a current need for a well-powered, prospective trial.

Revision Date: July 13, 2018

Our long-term goal is to develop, optimize, and disseminate treatments to improve CVD outcomes of a large cohort of patients at elevated risk of CVD onset, poor CVD prognosis, and high healthcare costs. This project's objective is to test whether our modernized IMPACT intervention (eIMPACT), delivered before CVD onset, reduces CVD risk. We propose a Phase 2 randomized controlled trial of 220 primary care patients (≥ 50 years, 40% African American) with a depressive disorder and CVD risk factors but no clinical CVD. Patients will be randomized to 12 months of eIMPACT (a collaborative stepped care program including antidepressants and computerized and telephonic cognitive-behavioral therapy) or usual care (usual primary care for depression). Patients will be followed for a mean of 4 years. The primary outcome is endothelial dysfunction assessed by brachial flow-mediated dilation (FMD),⁸¹ which is considered a barometer of CVD risk.⁸⁸ Critically, intervention-related improvements in FMD predict a reduced incidence of CVD events.¹¹³⁻¹¹⁵ Our central hypothesis is that eIMPACT will improve endothelial dysfunction in depressed patients by decreasing depressive symptoms, autonomic dysfunction, systemic inflammation, and platelet activation, which are leading candidate mechanisms. We will test our central hypothesis by carrying out these specific aims:

Aim 1: Determine whether eIMPACT reduces the excess CVD risk of depressed patients. Depressed patients randomized to eIMPACT, versus usual care, will exhibit a clinically and statistically significant improvement in the primary outcome of endothelial dysfunction at the 12-month post-treatment visit (Hypothesis 1). We will also explore whether eIMPACT patients, versus usual care patients, show a clinically relevant reduction (25% lower relative risk^{156,157}) in CVD events (exploratory outcome) over a mean observation period of 4 years (1-year intervention period plus 3-year follow-up period).

Aim 2: Examine candidate mechanisms underlying the effect of eIMPACT on CVD risk. Depressed patients randomized to eIMPACT, versus usual care, will exhibit greater decreases in the secondary outcomes of depressive symptoms (Hypothesis 2), autonomic dysfunction (Hypothesis 3), systemic inflammation (Hypothesis 4), and platelet activation (Hypothesis 5) at the 12-month post-treatment visit. We will also explore whether decreases in these four candidate mechanisms (a) are associated with improvements in endothelial dysfunction and (b) are partial mediators of eIMPACT's hypothesized cardioprotective effect.

A positive trial would generate the mechanistic rationale, efficacy evidence, and effect size estimates needed to justify and design a multisite, event-driven Phase 3 trial to confirm eIMPACT's efficacy in reducing CVD risk. Conversely, a negative trial would indicate a need to evaluate alternative approaches to reducing the excess CVD risk of depressed patients. Demonstrating that depression treatment reduces CVD risk, the main expected outcome of this line of research, would have a substantial positive impact. It would identify a novel target (depression) for CVD prevention efforts, and it would equip providers with a new disseminable and scalable tool (eIMPACT) to treat depression and manage the CVD risk of a large cohort of high-risk patients. These clinical practice changes should translate into reduced CVD morbidity, mortality, and costs, as our preliminary results suggest that treating 1,000 depressed adults may prevent 164 CVD events over 5 years.³⁵

3.0 Inclusion/Exclusion Criteria

Inclusion criteria

- Primary care patients
- Age ≥ 50 years
- Current depressive disorder
- Elevated CVD risk

To identify patients with a current depressive disorder, ResNet assistants will administer the PHQ-9,¹⁵⁸ a validated diagnostic measure designed for primary care patients.¹⁵⁹⁻¹⁶² We will consider patients to have a depressive disorder if (a) they have a PHQ-9 ≥ 10 ¹⁵⁸ and (b) they meet criteria for a PHQ-9 depressive disorder diagnosis (2 or more of the 9 depressive symptoms, including depressed mood or anhedonia, present in the past two weeks).¹⁶⁰ The cut point of ≥ 10 has 88% sensitivity and 88% specificity for MDD diagnosed by a clinical interview.¹⁵⁸ The combination of a PHQ-9 ≥ 10 and a PHQ-9 depressive disorder diagnosis helps to ensure that false positives will not be enrolled. In addition to its diagnostic validity, we chose a PHQ-9 case finding approach because: (a) it is feasible in primary care and is how depressed patients will likely be

identified in clinical practice, (b) recent successful trials have used similar approaches,^{31,60,163} and (c) we observed evidence of a signal of depression treatment on endothelial function and inflammation in our pilot trial, in which we used the PHQ-9.

Elevated CVD risk will be defined as ≥ 1 (if 60+ years) or ≥ 2 (if 50-59 years) of the following risk factors in the medical record in the past 5 years but no clinical CVD: hypertension, hypercholesterolemia, diabetes, or current smoking. According to the Framingham risk calculator for primary care patients,¹⁶⁴ the odds of a CVD event of a 50-year-old man/woman with 2 risk factors is about equivalent to that of a 60-year-old man/woman with 1 risk factor.

Exclusion Criteria

- History of clinical cardiovascular disease
- Presence of the following chronic disorders: HIV/AIDS, chronic kidney disease, or active cancer/current cancer treatment
- History of bipolar disorder or psychosis
- Continuous (e.g., daily) treatment for a systemic inflammatory condition (e.g., rheumatoid arthritis, lupus, Crohn's disease, and ulcerative colitis) in the past 3 months. Nonsteroidal anti-inflammatory drug (NSAID) use is allowed, given its high prevalence in the target population.
- Current use of anticoagulants (Aspirin and cholesterol and blood pressure medications are allowed.)
- Acute risk of suicide
- Severe cognitive impairment (≥ 3 errors on 6-item cognitive screen¹⁶⁵)
- Current pregnancy
- Ongoing depression treatment with a psychiatrist outside of the Eskenazi Health/Midtown system (ongoing depression treatment with a Eskenazi Health/Midtown psychiatrist is allowed, as we will be able to collaborate and coordinate depression care)

A history of clinical CVD will be defined as any of the following in the medical record before enrollment: CAD (ICD-9 410-414, 429.2) or CBV (ICD-9 430-434) diagnosis, acute MI (CK-MB >3.0 ng/ml or troponin >0.3 $\mu\text{g/L}$), percutaneous coronary intervention (ICD-9 00.66, 36.03, 36.06, 36.07, 36.09; CPT 92980-92984, 92995, 92996), or coronary artery bypass graft (ICD-9 36.10-36.19; CPT 33510-33536).

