1.0 Background

Significance

CVD and depression are top public health concerns; they are highly prevalent, deadly, and costly.

CVD is highly prevalent and disproportionately affects older adults.¹ A total of 15.4 and 6.8 million Americans suffer from coronary artery disease (CAD) and cerebrovascular disease (CBV).¹ CVD is also deadly. CAD and CBV are the first and fourth leading causes of death in the U.S.² Finally, the economic burden of CVD is substantial. For 2009, total cost in the U.S. was estimated to be \$312.6 billion, which is greater than all cancers.¹ Furthermore, due to the rapidly growing elderly population, the prevalence of CAD and CBV are projected to increase by 18-22% by 2030, and the total cost is expected more than double.¹

Depression is also a top concern. In the U.S., major depressive disorder (MDD) has a lifetime prevalence of 16.2%,³ and the point prevalence of depressive disorders in primary care is 16-19%.^{4,5} Depression is the leading cause of disability,⁶ and the annual total cost of depression is over \$83.1 billion.⁷ By 2020, CVD and depression are projected to be the #1 and #2 causes of disease burden worldwide.⁶

Depression is an independent risk and prognostic factor for CVD.

Thirty years of evidence indicates that depression is an independent risk and prognostic factor for CAD and CBV.^{8,9} Meta-analyses have shown that adults with a depressive disorder or symptoms have a 64% greater risk of CAD onset^{10,11} and that depressed CAD patients have a 59% greater likelihood of a future CVD event than their nondepressed counterparts.⁹ The depression-CVD relationship is comparable in strength to conventional CVD risk factors¹² and has been detected in men and women and in various age and racial/ethnic groups.^{8,13-15} Although other emotional factors have been linked to CVD,¹⁶ the depression association is the most consistently observed¹⁶ and seems to be independent of anxiety and hostility/anger.¹⁷ CVD risk increases with depression severity,¹⁰ indicating a dose-response relationship. Finally, depression has been linked to several atherogenic factors, which supports the biological plausibility of these prospective associations.

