4.0 Enrollment/Randomization

We will use the 3-stage process of our past trials to recruit patients. First, the Regenstrief Medical Records System,¹⁶⁶ one of most comprehensive electronic medical records, will be searched in accordance with HIPAA to generate lists of eligible patients. Next, ResNet assistants will obtain permission to approach from each patient's provider. ResNet, Indiana University's primary care practice-based research network, is the sole mechanism through which patients in the targeted clinics can be contacted for research. ResNet also maintains a patient registry, which will also be used by ResNet to identify potentially eligible patients. Finally, ResNet assistants will conduct high-intensity in-clinic and telephone screening and will enroll eligible patients (see Appendix 1 for Screening Interview). ResNet assistants will use a paper copy or a REDCap version of the Screening Interview. Through administering the eligibility interview refined in our pilots, ResNet assistants will assess cognitive function, medical/psychiatric status, and depression status; will obtain consent and authorization; and will implement the suicidal ideation protection protocol.

We estimate that $\approx 4,320$ patients (45/week) will need to be approached, consistent with the IMPACT trial.³⁶ We will be able to start recruitment immediately, as the infrastructure, personnel, and protocols are in place from the PI's recent trials. At the Indiana sites of the IMPACT trial, 6.4% of approached patients were randomized. We conservatively estimate that 5% of approached patients will be randomized (9/month) in the proposed trial. Patients who meet inclusion/exclusion criteria and consent will be scheduled for the pre-treatment visit. Because only patients who attend this visit will be randomized, it will serve as a prerandomization compliance screening.¹⁶⁷

In the unanticipated event of slower-than-projected recruitment, we will first request direct referrals from providers in the targeted clinics. Next, we will pursue expanding recruitment to another healthcare system in Indianapolis, such as the VAMC or Community Health Network. Finally, we will extend the recruitment window up to a year if the benefits to the primary outcome of endothelial dysfunction (ample power due to a larger sample) outweigh the costs to the exploratory outcome of CVD events (shorter observation period).

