Our exploratory outcome, modeled after the JUPITER trial,¹⁹⁵ is time to first major CVD event, defined as: CVD death (ICD-10 I20-I25 or I60-I69 the first-listed cause of death); nonfatal MI (CK-MB >3.0 ng/ml, troponin >0.3 µg/L, or ICD-9 410); nonfatal stroke (ICD-9 430-432, 433.01, 433.11, 433.21, 433.31, 433.91, 434.01, 434.11, 434.91); unstable angina requiring hospitalization (inpatient admission ICD-9 411.1); and revascularization – i.e., percutaneous coronary intervention (ICD-9 00.66, 36.03, 36.06, 36.07, 36.09; CPT 92980-92984, 92995, 92996) or coronary artery bypass graft (ICD-9 36.10-36.19; CPT 33510-33536). Because recruitment will occur during Years 01-02, the mean observation period will be 4 years (1-year intervention period plus 3-year follow-

up period), with a range of 3-5 years. The Regenstrief programmer who worked on our IMPACT study³⁵ will identify candidate CVD events by searching the INPC every 6 months (blind to assignment), with the last search performed on the end date. To capture the small number of events that may occur outside of the INPC catchment area, patients will complete a CVD questionnaire at mid- and post-treatment and during the follow-up calls. If a reported event is not in the INPC, we will request medical records from the patient to confirm the event. Our cardiologist ([name]), also blinded, will use standardized criteria to adjudicate all CVD events for this exploratory outcome. [name] has served on endpoint committees for past trials. When needed, [name] will consult with the cardiologist on the DSMB (also blinded). Given that we are coding “harder” events and that many events will be positive for multiple markers, it is unlikely that coded events will be misclassified. We may fail to detect (and thus initially misclassify) a few events through INPC, which is why we are obtaining patient reports and medical records.

Atherogenic Behavioral Factors

The BRFSS Tobacco Use Questionnaire, International Physical Activity Questionnaire, and the Morisky Questionnaire (MMAS-8) will assess tobacco use, physical activity, and adherence to cholesterol and blood pressure medications, respectively. Each scale possesses strong psychometric properties.¹⁹⁶⁻¹⁹⁸

Conventional CVD Risk Factors

SBP and DBP will be the mean of the last 2 of 3 readings.¹⁹⁹ Fasting cholesterol, glucose, insulin, and HbA1c will be quantified using standard methods. BMI will be computed from measured height and weight.

Miscellaneous Factors

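### The CVD-history rule stops at ICD-9 434 for cerebrovascular disease, so a patient whose only stroke entry is 436 or 438 can be enrolled as free of clinical CVD

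*Combined protocol and SAP*

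**What the plan says.** Section 3.0 of the combined protocol and SAP lists as an exclusion "History of clinical cardiovascular disease". It then makes this operational: "A history of clinical CVD will be defined as any of the following in the medical record before enrollment". The items are diagnosis codes, cardiac biomarkers and revascularization codes. The diagnosis item reads "CAD (ICD-9 410-414, 429.2) or CBV (ICD-9 430-434) diagnosis". There is no limit on how far back the record is read.

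Section 1.0 introduces the abbreviations as "coronary artery disease (CAD) and cerebrovascular disease (CBV"), so CBV stands for cerebrovascular disease as a whole.

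Section 5.0 (CVD Events) defines the exploratory outcome. Its fatal part is "CVD death (ICD-10 I20-I25 or I60-I69 the first-listed cause of death"). Its stroke part is "nonfatal stroke (ICD-9 430-432, 433.01, 433.11, 433.21, 433.31, 433.91, 434.01, 434.11, 434.91"). A blinded cardiologist adjudicates all events.

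Section 4.0 describes recruitment in three steps: a record search, provider permission to approach, and a screening interview. In the interview, "ResNet assistants will assess cognitive function, medical/psychiatric status, and depression status". The interview form is Appendix 1, which is not in the available text.

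**The concern.** The list treats old heart disease and old stroke differently. The coronary range 410-414 includes old MI (412), and 429.2 is added from outside that range. The cerebrovascular range ends at 434 with nothing added. A stroke treated elsewhere or long ago, and carried in the primary care record only as 436 or 438, meets no cerebrovascular item. By the written definition that patient has no clinical CVD.

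What is at stake is the population. The trial asks whether treating depression before clinical CVD lowers CVD risk. Section 2.0 says of the earlier follow-up study: "There was no treatment effect among patients with baseline CVD". Section 1.0 gives the depressive-symptom effect size in that study as 0.06 with baseline CVD and 0.69 without. By the plan's own evidence, patients with prior CVD are the group it means to keep out. Any who enter also contribute to the event estimates intended to inform a Phase 3 design.

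**Working it through.** **Code lists side by side.** The meanings of 412, 436 and 438 are not printed in the documents. They come from the ICD-9 classification that the rule itself invokes.

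| Record entry before enrollment | Item in the section 3.0 list | Status under the rule |
|---|---|---|
| Old MI, 412 | inside 410-414 | excluded |
| Stroke, 434.91 | inside 430-434 | excluded |
| Ill-defined stroke, 436 only | none | no clinical CVD |
| Late effects of stroke, 438 only | none | no clinical CVD |

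**History list against outcome list.** The nonfatal-stroke outcome uses three-digit categories 430, 431, 432, 433 and 434. Removing the exclusion categories 430-434 leaves nothing. The exclusion is in fact wider, because it takes all of 433 and 434 and the outcome takes only selected codes. The outcome range reaches beyond the history range only for deaths, in the ICD-10 block I60-I69.

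**Number of patients (assumed inputs).** The documents give neither the prevalence of past stroke nor how it is coded. Assume that 4-10% of candidates have had a stroke, that 15-40% of those carry only codes outside 430-434, and that the provider and interview steps catch none of them.

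- Low: 0.04 × 0.15 = 0.006; 220 × 0.006 = 1.3 patients.
- High: 0.10 × 0.40 = 0.04; 220 × 0.04 = 8.8 patients.

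**Share of events.** The plan's figure reproduces: 0.20 × 194 = 38.8, stated as 39. Assume a 4-year event rate in these patients between the plan's 20% and 40%.

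- Low: 1.3 × 0.20 = 0.3 events; 0.3 / 39 = about 0.7%.
- High: 8.8 × 0.40 = 3.5 events; 3.5 / 39 = about 9%.

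These are all events in such patients, including genuinely new ones after randomization.

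**FMD power.** The plan gives power 0.98 for d = 0.61 with 172 completers (86 per arm). By the normal approximation, 0.61 × √(86/2) = 4.00; 4.00 − 1.96 = 2.04; power is 0.979, which reproduces it. If the affected patients are spread evenly over the arms and gain no FMD benefit:

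- Low share: 0.61 × (1 − 0.006) = 0.606.
- High share: 0.61 × (1 − 0.04) = 0.586. Then 0.586 × √(86/2) = 3.84; 3.84 − 1.96 = 1.88; power is about 0.97.

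**The case against.** The case against rests on five arguments.

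- **Other steps precede enrollment.** Provider permission and an interview on medical status come first, and medical history is collected at the pre-treatment visit, before randomization. A reader might infer from the code list that stroke survivors will be enrolled. The documents do not support that, because Appendix 1 cannot be seen and may ask about stroke. This part stands, so the claim is only that such a patient can be enrolled. On the other side, the provider step is described as permission to approach, not an eligibility check, and the visible definition of CVD history relies on the medical record alone.
- **The outcome and history lists largely agree.** A reader might infer a general mismatch between them. There is none for nonfatal stroke. A first-listed cause-of-death block in ICD-10 serves another purpose and need not mirror an ICD-9 history list. This stands.
- **Adjudication.** A reader might infer that a death from the sequelae of an old stroke would be scored as an incident event. All events go to blinded adjudication under standardized criteria that are not reproduced, so this cannot be asserted.
- **No look-back limit.** Any 430-434 entry at any date excludes the patient. The gap therefore needs a survivor with no such entry, typically one treated elsewhere or long ago. This limits the size of the gap but does not close it. Section 5.0 allows for outcome events outside the network's catchment area by adding patient reports and outside records. The visible eligibility text describes no equivalent for baseline history.
- **Small and unquantified.** The count is assumed, the event outcome is exploratory, and the trial is not powered for it. This stands and sets the priority.

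**Conclusion.** The gap in the definition is real but narrow. As written, a patient whose only cerebrovascular entry is 436 or 438 counts as having no clinical CVD, while a patient with old MI does not.

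The number affected is unknown. The range of about 1 to 9 of 220 rests on assumed prevalence and coding shares, and on no other screening step catching anyone. Within that range, such patients would supply 0.3 to 3.5 of the 39 expected events. That figure does not measure old disease counted as new. Only deaths attributed to a pre-randomization stroke would be that, and their number cannot be estimated from the documents.

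A reader might also infer bias between the arms. The history is fixed before randomization, so by itself it does not bias the comparison. FMD power barely moves (0.98 to about 0.97 at worst). What is affected is the claim that the sample is free of clinical CVD, and the composition of the exploratory event analysis. This is a low-priority correction.

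**What to change.** In section 3.0, add ICD-9 436 and 438 to the cerebrovascular history codes, so that old stroke is handled like old MI. Whether 435 should also exclude can be left to the investigators.

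For patients already randomized:

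1. Run the extended list on records dated before randomization.
2. Keep every randomized patient in the intent-to-treat analysis.
3. Repeat the 12-month FMD comparison and the Cox model without the flagged patients, as a sensitivity analysis, and report how many were flagged.

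The cost is one line in the code list, one extra run of an existing query, one sensitivity analysis, and a few fewer eligible patients.
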